9.3 Phase 2: intervention implementation

Patients that are still enrolled in the health plan during 2017-2018 will be included in phase 2. Patients will be categorized by their adherence trajectory identified in phase 1 and will be randomized to intervention vs. not within each category. The proposed intervention will be a telephone call by a pharmacy student participating in rotations at Cigna-Health Spring Plan and trained in MI and 6 monthly follow up calls. During implementation, students will first examine the patient adherence pattern that was identified in phase 1 which will be coded. The student will then confirm the diagnosis, medication name, and dose with the patient answering the call and will follow the outlined protocol. Using MI, students will assess readiness for change, help patients identify potential barriers in accordance with patient past pattern of use, and guide them to develop a plan to deal with these barriers

A motivational interviewing intervention customized by patient adherence patterns (NCT03985098) – 03.28.2018

Additionally, the students will ask the 2 questions from the Patient Health Questionnaire (PHQ)-2, a validated screening tool for depression (attached). If the patient responds positively to either question, the student will suggest that the patient schedules an appointment with his/her healthcare provider to discuss these symptoms. The Supervising pharmacists will be available to assist the students in answering any medication related questions that may arise during the calls and arrange for a diabetes educator to contact the patient at a later time if needed. Follow up phone calls will be performed each month for a total of six calls. Students will be supervised by the pharmacist preceptors and managed care pharmacy residents throughout the calls and intervention implementation. The students who will be implementing the calls will attend a three day MI training facilitated by [name], who is experienced in utilizing motivational interviewing to improve adherence. The students will practice calls as a part of their training. They will also complete Human Subjects Research training before their rotation at Cigna Healthspring, and the certificates will be uploaded to the IRB application. After each initial call, students will record the date and write a summary of the interaction with the patient documenting the main barrier/s identified in the conversation and the plan made with the patient. During the follow up calls, students will emphasize the information, confirm problem solved, provide further encouragement and reinforce adherence.

Control group: For every patient that received a call, a control will be randomly selected from the list of patients randomly assigned to the control group.

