4.0 Vulnerable Populations

4.1 N/A

5.0 Number of Subjects

- 5.1 This study will have two phases. In the retrospective analysis stage, Cigna Healthspring will provide data on patients who fulfill eligibility criteria mentioned above. It is expected that this data will have approximately 22,000 patients with DM and HTN.
- 5.2 In the intervention phase, 250-300 patients will be included in the intervention phase. If 1 control is used for each patient in the intervention group, the total sample of phase 2 is expected to be 500-600.

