7.0 Study Timelines

- 7.1 The duration of the total study will be 3 years. Retrospective analysis of phase 1 and intervention development will require 12 months. The retrospective analysis will use data from July2016-January 2018. July – December 2016 will be used for baseline covariate measurement. January 2017- January 2018 will include adherence measurement. However this is de-identified patient data used for retrospective analysis and does not require patient participation.
- 7.2 The phase 2 of the study will involve the intervention call provided in the day of consent followed by monthly follow-up calls for six months. The patient however can refuse to participate in any of the calls, even if the patient has completed the primary phone call
- 7.3 The number, frequency and length of study visits: One intervention call lasting 12-15 minutes on average. Monthly follow up calls to the patients who received the initial call for six months lasting on an average for 5-10 minutes.(First call + 5 follow-up calls)
- 7.4 The duration anticipated to enroll all study subjects: The enrollment will continue for a period of 8 months (equivalent to an 2 active semesters)
- 7.5 The estimated date for the investigators to complete this study: 3 years Timeline details below

**A motivational interviewing intervention customized by patient adherence patterns
(NCT03985098) – 03.28.2018**

	Pre-award	Study Period: 36 months																	
		1 2	3 4	5 6	7 8	9 10	11 12	13 14	15 16	17 18	19 20	21 22	23 24	25 26	27 28	29 30	31 32	33 34	35 36
IRB Approval																			
Phase 1 trajectory modeling																			
Intervention Development																			
MI training and randomization																			
Intervention implementation																			
Post intervention analysis																			
Manuscript / Final report prep																			

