20.0 Data Management

- 20.1 The data which will be provided by Cigna will contain data with encrypted patient IDs. The electronic data files for this study will be processed on a dedicated, layered-security server, which can be accessed only by [name] and designated project staff members who are under the direct supervision of [name]. Since the system is behind multiple firewalls, is monitored regularly, and is accessible only to key personnel, the risk of unlawful penetration is not a significant data safeguard concern. Data will be stored on the secure server for 3 years following the completion of the study. All analysis will be conducted on the desktop at UH College of Pharmacy. The data will not be accessible through any personal computers.

SAS 9.4 is the statistical software, which will be used for the analysis.

A motivational interviewing intervention customized by patient adherence patterns (NCT03985098) – 03.28.2018

Baseline characteristics: Comparisons in baseline characteristics will be made between the 2 study groups (intervention vs. control) using t-tests for continuous variables and chi-square tests for categorical variables. The characteristics evaluated will include predisposing factors: demographics, and number of other medications used; enabling factors: health plan (LIS vs. not), prescriber specialty (specialist vs. primary care); need factors: comorbidities (CHF, MI, CAD, stroke, ESRD, depression), previous hospitalization and CMS risk score.

Baseline PDC in the 12 months prior to intervention and patient past adherence trajectory will also be compared between 2 groups. Because of the randomization, we do not anticipate any significant differences between the two study groups on these characteristics.

Outcome analysis: Refill data during 2 time periods -- 6, and 12 months, following the initial call of the intervention will be evaluated to calculate adherence rates for both the intervention and control groups. The two periods were chosen to evaluate the intervention effect during the 6 months when the follow up calls were ongoing as well as after these calls had stopped. The adherence rate will be defined as proportion of days covered (PDC) for six and twelve month follow up period following the intervention. An intent to treat analysis will be utilized.

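### The number randomised in Phase 2 is not linked to the 250-300 planned calls, and the groups built from call completers conflict with the promised intent-to-treat analysis

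*Combined protocol and SAP*

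**What the plan says.** Section 5.1 describes the Phase 1 source data: "It is expected that this data will have approximately 22,000 patients with DM and HTN". Section 5.2 says that "250-300 patients will be included in the intervention phase" and, with one control for each, "the total sample of phase 2 is expected to be 500-600". Section 7.4 adds: "The enrollment will continue for a period of 8 months".

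On who is randomised, section 9.3 states: "Patients that are still enrolled in the health plan during 2017-2018 will be included in phase 2". These patients are sorted by trajectory and "will be randomized to intervention vs. not within each category". Section 2.1 restricts Phase 2 to non-adherent patients; section 9.3 does not repeat this. No section gives the number randomised, the allocation ratio or the order of calling.

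On who forms the groups, section 6.2 counts a patient in the intervention group once he or she has consented and completed the call. The control-group paragraph of 9.3 says that for each patient called, "a control will be randomly selected from the list of patients randomly assigned to the control group".

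On analysis, the outcome paragraph of section 20.1 measures adherence from the initial call and states: "An intent to treat analysis will be utilized". It does not say which patients make up that analysis set.

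**The concern.** Three parts of the plan do not fit together: an allocation step with no stated size, groups defined by what happened after allocation, and an analysis principle that requires everyone allocated to be kept.

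If the team follows the group definitions, it compares people who could be reached, agreed and finished a call with controls who passed no such filter. Such people may well refill better anyway, so the bias probably favours the intervention and the protection of randomisation is lost.

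If the team follows the intent-to-treat statement, it must include every patient assigned to intervention. Nothing keeps that list close to the number students can attempt. A long list would consist largely of patients who were never called, and the contrast would shrink accordingly.

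Correcting the analysis set alone would therefore exchange the first problem for the second. A full intent-to-treat analysis also lacks a start date: follow-up runs from the initial call, and neither uncalled patients nor controls have one. Objective 8.3 rests on this comparison.

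**Working it through.** **The plan's own figure.** 2 × 250 = 500 and 2 × 300 = 600, so the stated total of 500-600 reproduces. It equals completers plus one drawn control each. There is no power calculation to reproduce: alpha, power, effect size and standard deviation are not given.

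**Inputs from the documents.** Source cohort about 22,000 (5.1); planned intervention patients C = 250-300 (5.2), who under 6.2 are patients with a completed call.

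**Assumptions.** Eligible share f of the 22,000; 1:1 allocation; PDC standard deviation 0.30; true gain of 10 PDC points in called patients and none in uncalled patients; two-sided 5% test, normal approximation.

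**Everyone on the eligible list randomised and analysed.**
- n per arm = 22,000 × f / 2
- treated share p = C / n
- intent-to-treat difference = 10 × p points
- standard error = 0.30 × √(2/n)

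| f | n per arm | p (C = 250 to 300) | Difference, points | Power |
|---|---|---|---|---|
| 5% | 550 | 45.5-54.5% | 4.5-5.5 | 71-85% |
| 10% | 1,100 | 22.7-27.3% | 2.3-2.7 | 43-57% |
| 20% | 2,200 | 11.4-13.6% | 1.1-1.4 | 24-33% |
| 50% | 5,500 | 4.5-5.5% | 0.5 | 12-16% |

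Example, f = 10% and C = 300: p = 300/1,100 = 0.273; difference 2.73 points; standard error 0.30 × √(2/1,100) = 1.28 points; ratio 2.13; power 57%.

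**Only patients who will be attempted are randomised.** With completion rate r, n = C / r per arm and the difference is 10 × r points.
- r = 0.4: 625-750 per arm, 4 points, power 65-73%
- r = 0.6: 417-500 per arm, 6 points, power 82-89%

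**When most of the assigned arm would go unattempted.** Attempts number C / r. Half of the intervention arm is N/4 when N patients are randomised 1:1, so the threshold is N = 4C / r.
- r = 1: 1,000-1,200 patients, 4.5-5.5% of 22,000
- r = 0.5: 2,000-2,400, 9.1-10.9%
- r = 0.3: about 3,330-4,000, 15.2-18.2%

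**Sensitivity to effect size.** Take instead 0.229 standard deviations in called patients, which gives 80% power with 300 per arm all called. With 300 completed calls, analysing everyone randomised then has power of about 31%, 18% and 11% at f = 10%, 20% and 40%. Arms matched to attempts have about 51% at r = 0.5 (600 per arm) and 34% at r = 0.3 (1,000 per arm). The direction is the same, but matching the arm to attempts does not restore full power.

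**The written group definitions.** With completers and one drawn control each (250-300 per arm), uncalled patients are not analysed. There is then no dilution from them, but there is selection.

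**The case against.** The strongest reply is that the dilution is not in the plan as written. Sections 5.2, 6.2 and 9.3 consistently describe 500-600 analysed patients, none of them uncalled intervention patients. That is right, and it means dilution is only one of two outcomes. It does not rescue the plan, because those groups are not an intent-to-treat comparison.

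A reader might infer that most of the intervention arm will never be attempted. The documents do not establish this:
- The eligible share is not given. The 22,000 may precede exclusions, since section 3.2 applies the criteria during data analysis, and the pool then narrows to non-adherent, still-enrolled patients taking the medication. At 5% eligible, power is already within the range obtained when only attempted patients are randomised.
- Drawing controls from a longer list shows surplus controls. It does not show a surplus intervention list, because the ratio is unstated and a well-sized 1:1 allocation with 50% completion would also leave spare controls.
- 250-300 is a planned count, not a stated calling capacity.
- No passage says that callers choose whom to dial by convenience. The timeline in section 7 lists randomisation and implementation as separate rows, but its bars cannot be read, so allocation in one step before calling is not shown.

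It can also be said that stating the number allocated and a random calling order would be enough. That would limit the dilution, but on its own it would neither replace the completer-based groups nor give uncalled patients and controls a start date.

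**Conclusion.** The point holds in a conditional form. The number assigned to intervention is not tied to the planned 250-300 completed calls, no calling order is given, and the group definitions in 6.2 and 9.3 contradict the intent-to-treat statement in 20.1. As written, the trial gives either a selected comparison, probably biased towards the intervention, or an all-randomised comparison whose dilution grows with the length of the eligible list.

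The contradiction is certain from the text; the size of the dilution is not. It rests on the assumed eligible share, 1:1 allocation, standard deviation and gain, and ranges from little loss at 5% eligible to a largely uninformative trial at 20-50%. The claim that the effect will be diluted towards zero goes further than the documents allow. The matter should be settled before allocation, because the choice of whom to randomise cannot be repaired afterwards.

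**What to change.** In section 9.3:
- Put eligible patients in a computer-generated random order within each trajectory, and state whether eligibility is limited to non-adherent patients, as in section 2.1.
- Randomise to intervention or control in batches sized to what students can attempt, just before each batch is called. State the allocation ratio.
- Attempt every intervention patient in a released batch. Stop at the end of the batch in which the 250-300 target is met. Patients never released are not randomised.

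In sections 6.2, 9.3 (control group) and 20.1:
- Replace the completer and drawn-control definitions. The intent-to-treat set is all patients in released batches, both arms.
- Start the 6- and 12-month PDC windows at the batch release date in both arms.
- Revise the 500-600 total in section 5.2 for the expected completion rate. With 40-60% completing, 250-300 completed calls correspond to 417-750 per arm.

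The cost is protocol wording and an allocation list held at the health plan. The allocation step is repeated for each batch, and some further call attempts may be needed to finish the last one. Dilution from patients who are attempted but do not complete a call remains and should be allowed for in the sample size.

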6.0 Recruitment Methods

LOCAL:

- 6.1 This study will start with the retrospective phase which does not involve recruitment of patients, but involves analysis of existing data. De-identified data will be obtained from Cigna-Healthspring.
- 6.2 The project will be implemented in collaboration with Cigna-Health Spring, a Medicare Advantage Plan in Texas. The health plan has several electronic data files available for analysis including membership file, member

A motivational interviewing intervention customized by patient adherence patterns (NCT03985098) – 03.28.2018

summary file, institutional claims file, professional claims file, quest lab, Cigna-Health Spring's medical claims file (CCMS) and pharmacy file. Pharmacy files contain Part D pharmacy data provided by pharmacy benefits manager including patient/ drug identifying information, fill dates, days of supply, quantity dispensed and dosing for each prescription filled. The refill data will be used to determine the non-adherent patients. ICD-10 codes will be used to determine other exclusions using professional claims data.

Phase 2 will involve project intervention which will be conducted over the phone. A list of actively enrolled members, taking the medication who were a part of phase 1 will be created by Cigna HealthSpring to be used for intervention implementation at their premises. The phone call will be made by University of Houston pharmacy students who will be on rotation at Cigna-HealthSpring. The form of informed consent which will be read to the patient is attached to the IRB. If the patient consents to receive the intervention over the phone, and completes the phone call, the patient forms a part of the intervention group. Five follow-up phones will be attempted one month apart for the patient after the initial call.

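### Controls are not specified to come from the called patient's trajectory, so the stratified randomisation need not carry through to the arms compared, and the significance-triggered adjustment only partly corrects a moderate imbalance

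*Combined protocol and SAP*

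**What the plan says.** Section 9.3 stratifies the allocation: patients are grouped by phase 1 trajectory and "will be randomized to intervention vs. not within each category". Its control-group paragraph then states: "For every patient that received a call, a control will be randomly selected from the list of patients randomly assigned to the control group". Trajectory is neither required nor excluded as a condition of that draw.

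Section 6.0 defines who counts as treated. A patient who consents and "completes the phone call, the patient forms a part of the intervention group".

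Section 5.0 plans 250 to 300 intervention patients and adds: "If 1 control is used for each patient in the intervention group, the total sample of phase 2 is expected to be 500-600".

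Section 20.0 covers the baseline check: "Baseline PDC in the 12 months prior to intervention and patient past adherence trajectory will also be compared between 2 groups". It expects balance: "Because of the randomization, we do not anticipate any significant differences between the two study groups on these characteristics". PDC means at 6 and 12 months are compared by t-test, and the proportions with PDC of at least 80% by chi-square test. Multiple or logistic regression is used only if a baseline characteristic differs significantly. The same section calls the analysis intent to treat. Section 9.2 lists prior trajectory and baseline PDC among the model covariates and attaches no significance condition.

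**The concern.** Randomising within trajectory makes the two assigned groups alike in trajectory. The groups compared are not the assigned groups. One arm is the subset that completed a call. The other, on the plain reading of 9.3, is a simple random sample of the control list. The first has the trajectory mix of completers and the second the mix of everyone assigned to control. The two mixes agree in expectation only if completion is the same in every trajectory.

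Trajectory is built from monthly PDC indicators (Section 9.1) and the outcome is PDC, so trajectory should predict the outcome strongly. A difference in mix would then look like an intervention effect in the unadjusted comparison. It would favour the intervention if more persistent users complete more calls, and work against it if they complete fewer. The planned safeguard depends on a significance test, which can miss an imbalance large enough to matter.

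**Working it through.** **The plan's own figure.** 2 × 250 = 500 and 2 × 300 = 600, so the stated total reproduces. It is a count. The documents give no alpha, power, effect size, SD, trajectory shares or completion rates, so everything below is an illustration on assumed inputs with a two-sided 5% test and no true effect.

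**Assumed inputs.** Two trajectories of equal size; follow-up mean PDC 0.60 and 0.15; total SD 0.30; 275 per arm (the middle of 250 to 300). Completion is c1 in the higher-PDC trajectory and c2 in the lower.

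**Formulas.**
- Share of the higher-PDC trajectory among called patients: c1/(c1 + c2). Among controls it is 0.5.
- Bias of the unadjusted difference: (called share − 0.5) × (0.60 − 0.15).
- Standard error: 0.30 × √(2/275) = 0.0256, or 2.6 points.
- Expected z of the trajectory comparison: (called share − 0.5)/√(2 × 0.25/275), with denominator 0.0426.

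**Completion 40% versus 30%.** Called share 0.40/0.70 = 0.571. Bias 0.071 × 0.45 = 0.032, or 3.2/2.6 ≈ 1.25 standard errors, which gives the unadjusted t-test a type I error of about 24%. The expected z for imbalance is 0.071/0.0426 ≈ 1.67, so the test is significant in about 40% of trials. In the other 60% the mean bias is about 2.0 points. Averaged over the rule, the bias is 0.60 × 2.0 ≈ 1.2 points (about 0.5 standard errors), with type I error about 6%. Adjusting in every trial gives about 5%.

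**Completion 40% versus 20%.** Called share 0.40/0.60 = 0.667. Unadjusted bias 0.167 × 0.45 = 7.5 points. The imbalance test is significant in about 98% of trials, so the rule leaves about 0.1 points of bias and type I error near 5%.

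**Second set of assumptions.** Three trajectories with shares 40/30/30%, mean PDC 0.65/0.45/0.20, within-trajectory SD 0.20, 250 or 300 per arm, 20,000 simulated trials:

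| Completion by trajectory | Unadjusted bias | Type I, t-test | Type I, conditional rule | Type I, always adjusted |
|---|---|---|---|---|
| 40/40/40% | 0 | 5% | 4% | 5% |
| 42/40/37% | 0.010 | 7% | 5% | 5% |
| 45/40/33% | 0.023 | 16–19% | 8% | 5% |
| 50/40/25% | 0.049 | 53–61% | 6–8% | 5% |
| 50/35/15% | 0.077 | 91–95% | 5% | 5% |

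The conditional rule does worst at moderate imbalance (third row), where the trajectory test is significant in only 22–26% of trials.

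**With controls drawn within trajectory.** The two arms have the same trajectory mix, so this component of bias is 0 in every row. A plain t-test then becomes conservative (type I error about 0.7% to 1.5% in the second set), because it ignores the matching. The matched draw therefore needs the trajectory-adjusted model alongside it.

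**What that does not remove.** If completers and non-completers in the same trajectory differ in PDC by an assumed 0.05 to 0.15, the bias left is gap × (1 − completion rate): 0.03 to 0.09 at 40% completion and 0.02 to 0.06 at 60%.

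**The case against.** The strongest reply is that the plan already has protection. Section 20.0 compares trajectory and baseline PDC between arms and adjusts if they differ significantly, and Section 9.2 lists both as covariates unconditionally. This largely stands. A reader might infer that 7.5 points, or even the full 3.2, would reach the reported result. Under the plan's rule they would not: the large imbalance is nearly always adjusted for, and the moderate one is adjusted for in about 40% of trials. What survives is the moderate case, and the unresolved difference between 9.2 (trajectory listed without condition) and 20.0 (adjustment only on significance).

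The documents also do not say that completion differs by trajectory. The discussion in 9.2 of barriers concerns taking the medicine, not answering the telephone. That makes unequal completion plausible and no more. Nor is trajectory ranked anywhere as the strongest predictor of PDC. Reading 9.3 as an instruction to ignore trajectory turns silence into a rule; the accurate statement is that a within-trajectory draw is not specified.

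The 0.45 gap in mean PDC may be generous, since Section 6.0 describes the call list as members taking the medication, which could thin out discontinuers. Bias scales with the gap: at 0.20, the 40% versus 30% case gives 0.071 × 0.20 = 1.4 points unadjusted.

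Finally, it can be said that the draw is a symptom and that the larger fault is comparing completers with unselected controls under an intent-to-treat label. That is right, and it limits what the fix can claim. It does not make the draw harmless if control sampling is kept.

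**Conclusion.** The concern holds in a limited form. As written, 9.3 does not carry the trajectory strata into the control draw, so the balance expected in 20.0 does not follow from the randomisation once one arm is restricted to completers. The consequence depends on completion rates that the documents do not give. If completion is equal across trajectories there is no bias from this source, and small differences matter little. At a moderate difference the plan's conditional rule leaves about 1.2 points of PDC on average and type I error of about 6% under the first set of assumptions, and up to about 8% under the second. At a large difference little remains. The PDC of at least 80% outcome follows the same logic but was not quantified.

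This is a modest defect with a nearly free remedy. It should not be read as showing that the main result would be badly distorted by the draw, nor that drawing within trajectory would make the comparison sound. On the assumptions shown, the difference between completers and unselected controls within a trajectory could be larger (3 to 9 points at 40% completion).

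**What to change.** - **Section 9.3, control group:** state that each control is drawn at random from control-allocated patients with the same phase 1 trajectory code as the called patient. If more than one control per patient is kept, weight or stratify them to the intervention group's trajectory mix.
- **Section 20.0, outcome analysis:** include trajectory as a prespecified covariate in the PDC regression and the PDC of at least 80% logistic model, whatever the baseline test shows, and report these models as the main comparison. This also brings 20.0 into line with the covariate list in 9.2.
- **For the bias that these changes leave:** analyse all randomised patients as assigned, as the intent-to-treat statement implies. The stratified randomisation then stands intact and no control draw is needed. Adjustment for trajectory is still worth keeping.

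The first two changes cost a few sentences. The trajectory codes are already planned for every patient and the total stays at 500 to 600. The draw needs at least as many controls as completed calls in each trajectory; equal allocation within trajectory would give that, but the randomisation ratio is not stated and should be. Analysing everyone as assigned needs refill data on all randomised patients, so the planned total would have to be restated.
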